3.5 Subject Recruitment and Enrollment

Study subjects may be referred for surgical treatment of SUI by their primary care physician or specialist. Subjects must provide written informed consent prior to study-related procedures taking place. A screening and enrollment log will be maintained by study sites to document potential subjects who did not meet inclusion/exclusion criteria or who declined participation.

3.6 Point of Enrollment

Once the subject signs the approved informed consent form the subject is considered enrolled and a subject number is assigned.

3.7 Subject Withdrawal Criteria

The investigator may withdraw a subject from the study at any time if they judge withdrawal to be in the best interest of the subject for reasons including but not limited to the subject's safety and/or well-being.

Subjects are allowed to withdraw from the study at any time for whatever reason without any consequences to their future treatment outside the clinical study. If a participant expresses the desire to withdraw from the study, an end of study form must be completed. The reason for participant withdrawal must be documented.

In the case that the participant cannot be reached to return for protocol required follow-up visits, the study site must make at least 3 attempts to contact the subject (e.g. telephone, email). To be considered lost to follow-up, all attempts to contact the subject must be documented and a registered letter must be sent to the subject's last known address. In the case that the participant is determined to be lost to follow-up, an end of study form must also be completed.

If a subject withdraws, is lost to follow-up, or dies they will not be replaced by enrolling additional subjects. Participants will be considered to have completed the study after the 36-month follow-up visit has been completed.

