3.3 Endpoints

3.3.1 Primary Safety Endpoints

- Observed device and/or procedure-related serious adverse events through 36-months.

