5.6 Blinding

Study subjects and investigational study personnel are not blinded to study group assignment.

6 Identification and Description of Devices

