6.1 Description of the Study Device

Altis SIS is a permanently implantable synthetic sling for the surgical treatment of SUI. Altis SIS is made from a knitted, monofilament polypropylene with low elasticity. This structure gives Altis SIS resistance to traction, allows tissue in-growth and facilitates positioning during surgery. Altis SIS is placed at the mid-urethra to treat SUI by providing a scaffold for tissue in-growth and support for stress events.

Altis SIS is sterile, single-use only synthetic sling with left and right introducer needles. The specialized introducers allow the physician to position anchors in the obturator foramen through a single vaginal incision. The introducers can only be used with Altis SIS and are indicated for single use.

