14.1 Adverse Event/Complication Classification

Collection of Adverse Events will begin at the time the first incision is made for the index surgical procedure and will continue until the subject's study participation is complete. The investigator will be asked to assess the relationship of the event to the implanted study product, the implant study procedure, and the presence or performance of the mesh itself for each adverse event reported. Serious and non-serious adverse events will be collected and reported for this study.

The principal investigator will ensure that adequate medical care is provided to all subjects experiencing an adverse event during or after participation in the clinical investigation. Any ongoing adverse events must be assessed on an ongoing basis to determine resolution.

The current status of all ongoing adverse events is documented at the time of site close-out. The resolution date will be recorded on an adverse event eCRF.

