The primary analysis of this endpoint will include all available data and ‘presumed failures’ from the mITT analysis population. Presumed failures are defined as subjects with missing data where it is known that the cause of the data loss is either related (1) to an adverse event, including death, or (2) to a device failure. ‘Presumed failures’ will be considered failures for all primary effectiveness endpoint analyses. ‘Presumed failures’ will contribute available data up to the point of failure, and will be considered failures in the primary effectiveness endpoint analysis after the point of failure. Subjects with missing data for other reasons will be ignored in the primary analysis. As described above, the primary effectiveness endpoint will also be summarized for the PP analysis set, following the same logic as the main analysis in the mITT analysis set.

Sensitivity Analyses

The following sensitivity analyses will be performed on the primary effectiveness endpoint:

- An analysis utilizing multiple imputation (MI) for missing values will be performed for the primary effectiveness endpoint based on the mITT analysis population. Selection of variables for the MI analysis will be performed by first assessing the correlation of relevant baseline variables including, but not limited to: baseline age, investigational site, and baseline pad weight. The initial list of candidate variables may be adjusted to allow for proper model convergence. A total of 100 imputed datasets will be created to determine the imputed effect size.
- The primary effectiveness endpoint will also be assessed in the ITT analysis population. Again, multiple imputation method will be employed to impute missing values.
 - A comparison of relevant baseline and clinical variables between missing and non-missing subjects will also be used to assess the likelihood that missingness is differential or non-differential. Non-differential missingness with respect to the outcome is known to not bias results, but to attenuate a

given effect size. Should missing subjects and non-missing subjects demonstrate high concordance on baseline factors, it can be reasonably argued that missingness is non-differential and therefore results from complete case analyses are unbiased.

- Additional sensitivity analyses for the primary effectiveness endpoint will include best case, worst case and tipping point analysis, and will be based on the mITT analysis set.

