12.6.2. Primary Safety Analyses

Main Analysis

The number and proportion of subjects experiencing device- and/or procedure-related serious adverse events will be tabulated for each study group. Non-inferiority through 36 months will be calculated using a normal approximation test (Z-test) for a difference in binomial proportion. Non-inferiority will be achieved if the lower limit of the 95% confidence interval for the difference in proportions (Comparator – Altis) is greater than -0.10 in the mITT analysis population. If non-inferiority is achieved and the lower limit of the 95% confidence interval for difference in proportions (Comparator – Altis) is greater than 0, superiority of Altis can also be claimed. As this follows a simple closed test procedure, no multiplicity adjustment is necessary.

The primary analysis of this endpoint will include all available data from the mITT analysis population. Subjects that have not experienced a device- and/or procedure-related serious event and who have missing data at 36 months will be assumed to be free of such an adverse event.

Sensitivity Analyses

The potential impact on the endpoint inference of all subjects with missing primary safety endpoint data will be assessed via various sensitivity analyses that include best case, worst case and tipping point analysis. In addition, a Kaplan-Meier product limit analysis that right censors subjects lost to follow-up will be conducted to further understand the potential impact of subject loss. All sensitivity analyses will be based on the mITT analysis set.

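### Investigator-initiated withdrawal after implantation ends adverse-event and revision collection, and the woman is then scored event-free at 36 months

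*Protocol*

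**What the plan says.** Protocol 3.7 gives the investigator a power to withdraw: "The investigator may withdraw a subject from the study at any time if they judge withdrawal to be in the best interest". The grounds are left open: "for reasons including but not limited to the subject's safety and/or well-being". The withdrawal is from the study as a whole. The section does not distinguish stopping study tests and visits from stopping safety follow-up. It requires an end-of-study form when the participant asks to leave or is lost to follow-up, but does not say so for withdrawal by the investigator.

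Protocol 5.6 on masking: "Study subjects and investigational study personnel are not blinded to study group assignment". Protocol 6.1 on the device: "Altis SIS is a permanently implantable synthetic sling for the surgical treatment of SUI"; the two sponsor control slings in 6.2 are also described as permanent.

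The primary safety endpoint (Protocol 3.3.1) is: "Observed device and/or procedure-related serious adverse events through 36-months". Protocol 14.1 says that adverse-event collection "will continue until the subject's study participation is complete". Under SAP 12.6.2, women with no recorded related serious event "who have missing data at 36 months will be assumed to be free of such an adverse event". Protocol 7.5 has the same rule, and Protocol 7.6.1 and 7.6.2 and SAP 12.7.1 and 12.7.2 apply it to the two powered secondary safety endpoints.

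By contrast, Protocol 17 says that if the whole study is terminated, treated women should still be followed to their 36-month visit.

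**The concern.** The only study intervention is a sling placed at the index procedure. Withdrawing a woman later does not end her exposure unless the device is also removed, and 3.7 does not link the two. What ends is observation. If a woman is withdrawn because of her safety or well-being, she may be at higher risk of a later related serious event or revision than a woman who stays. The loss is then informative, and the person deciding knows which sling she has.

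The primary analysis fills the gap with the favourable value. A problem that becomes serious, or leads to revision, after exit is neither collected nor allowed for in the main estimate. This affects the primary safety and revision/resurgery endpoints most. It matters less for the endpoint of any related adverse event, because a problem already emerging at withdrawal will usually have been recorded and counted.

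Protocol 17 protects 36-month follow-up when the sponsor stops the study, but nothing comparable covers one investigator's decision about one woman.

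**Working it through.** **Plan's own figure.** Inputs from Protocol 7.9.3 and 7.9.5: 10% in each arm, margin 0.10, one-sided 0.025, power 80%.

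n = (1.960 + 0.842)² × (0.10×0.90 + 0.10×0.90) / 0.10² = 7.849 × 0.18 / 0.01 = 141.3, so 142 per arm. Allowing 20% attrition, 142 / 0.80 = 177.5, so 178. Both agree with the documents: 142 in SAP 10.2 and 178 in Protocol 7.9.3.

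**Decision rule (SAP 12.6.2).** Non-inferiority is declared if (pC − pT) − 1.96 × √[pC(1−pC)/178 + pT(1−pT)/178] > −0.10, with every woman in the denominator.

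**How close the rule can run.** With 18/178 comparator events, 23 Altis events give a lower limit of −0.0943 (pass) and 24 give −0.1006 (fail). One uncounted event can decide the result.

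**Effect of uncounted events.** The documents give no rate of investigator withdrawal, so the true rates and the numbers lost are assumptions. True rates are set at the margin: comparator 10%, Altis 20%. Losing k events on average in an arm lowers its observed rate by k/178: 2, 4 and 6 events are 1.12, 2.25 and 3.37 percentage points, so Altis appears as 18.88%, 17.75% and 16.63%. The probability of passing comes from exact enumeration over both binomial counts.

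| Events lost | 0 | 2 | 4 | 6 |
|---|---|---|---|---|
| Altis only | 2.7% | 5.2% | 9.5% | 16.1% |
| Same count in each arm | 2.7% | 2.8% | 2.8% | 2.9% |
| Comparator only | 2.7% | 1.3% | 0.6% | 0.2% |

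- Equal share lost: 10% of events in each arm makes the observed rates 9% and 18%. The difference shrinks from 0.10 to 0.09, and false non-inferiority is 5.0%.
- The table counts lost events, not withdrawn women. If only half of 2, 4 or 6 withdrawn Altis women would have had an event, the figures are 3.8%, 5.2% and 7.1%.
- With true rates of 5% and 15%, the Altis-only figures are 3.0% with no loss, then 6.5%, 12.8% and 23.0%. Losing 10% of events in each arm gives 6.2%.

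**The case against.** Several points on the other side stand.

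- A reader might infer that these women drop out of the safety comparison. They do not: they remain in the mITT denominator and events recorded before exit count. Only later events are missing.
- A reader might infer that all three powered safety endpoints are equally exposed. For any related adverse event they are not. Non-serious events are collected from first incision, and SAP 12.7.5 treats even a possible relationship as related.
- A reader might infer that the clause favours Altis. The documents do not support that, since no arm pattern is given and the table shows the effect can run either way.
- A reader might see a contradiction with the effectiveness rule in SAP 12.6.1, which begins: "Presumed failures are defined as subjects with missing data where it is known that the cause of the data loss is either related". The two causes it then names are adverse events and device failure. The contrast is worth noting, but it sets a 6-month effectiveness endpoint against a 36-month safety endpoint, so it is not an inconsistency.
- Best-case, worst-case, tipping-point and Kaplan-Meier analyses are planned, and SAP 12.3 summarises withdrawals and reasons. A scenario counting these women as events lies largely within that set.
- Protocol 14.1 also asks for ongoing events to be assessed for resolution, so the problem that prompted withdrawal may be tracked for longer.
- Consent pages and case report forms were not available and may cover access to records after withdrawal.

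The gap remains. Sensitivity analyses recover no data and are not the decision rule. Kaplan-Meier censoring assumes that loss is unrelated to later risk, which is doubtful when withdrawal is for safety. Nothing in the text provided requires collection of new events or revisions after the investigator withdraws a woman.

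**Conclusion.** The point holds as a gap in data collection. Protocol 3.7 and 14.1 together allow an unmasked decision to end event and revision collection in an implanted woman, and the missing-data rule then scores her event-free for the primary safety and revision/resurgery endpoints. That collection stops at withdrawal is inferred from reading the two sections together; nothing in the text provided contradicts it.

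The size cannot be stated from the documents. Under the assumed 10% and 20% rates, false non-inferiority ranges from 0.2% (6 events lost in the comparator only) to 16.1% (6 lost in Altis only), against 2.7% with no loss. Equal counts in both arms leave it almost unchanged, and equal 10% shares raise it to 5.0%. The 16.1% figure is one end of a scenario range and should not be read as an expected inflation. The case for change rests on how easily an avoidable, possibly informative loss can be prevented.

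**What to change.** - In Protocol 3.7 and 14.1, state that after an implant attempt, withdrawal by the investigator stops study tests and visits but not collection of adverse events and revision/resurgery. Collection continues by telephone or record review through month 36 unless the woman herself withdraws consent.
- Require the end-of-study form for investigator-initiated withdrawals too. Record who initiated the withdrawal and whether a suspected device or procedure problem was a reason. Report these withdrawals by arm.
- In SAP 12.6.2 and 12.7.2, include counting such withdrawals as events as one labelled scenario within the planned tipping-point analysis. No separate analysis is needed.

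The cost is protocol and form wording, occasional calls or chart checks, and possibly slightly higher event counts. The sample size is unchanged. If follow-up is already complete, recording who initiated each withdrawal and why, reporting by arm, and the labelled scenario are still feasible.

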3.8 Subject Retention

Subject follow-up visit compliance and long term retention of study subjects through 36-months is important. Every attempt should be made to complete the visit. If the follow-up visit cannot be completed within the established visit window, the visit should still be completed as soon as possible and a study deviation documented.

Additional strategies to maximize subject retention may include:

- Use of an IRB approved tiered subject visit compensation rate that increases over the course of the study
- Utilization of a follow-up window calculator tool to assist in targeting and scheduling future study follow-up visits
- Utilization of study specific appointment reminder cards and direct telephone contact

4 Total Expected Duration of the Clinical Study

Enrollment is expected to take approximately 2 years to complete and subjects will be followed for 36 months. The study will take approximately 5 years from first subject enrollment to final patient visit.

5 Procedures and Data Collection

Prior to site activation, all study personnel must receive formal study training from qualified personnel from Coloplast or its designee. This training will include, but is not limited to device design, clinical study protocol, case report form completion, regulatory requirements and required study procedures. Before initiation of the clinical study, the investigator must obtain Institutional Review (IRB) approval and the sponsor must be provided with a signed investigator agreement and dated curriculum vitae for key personnel to verify and document qualifications. The investigator must ensure that all site personnel are trained for delegated activities, e.g. study procedures, eCRF completion, and adverse event reporting.

Clinical data will be collected at baseline, procedure, 6 months, 12 months, 18 months, 24 months, and 36 months post index procedure. The Data Collection Schedule in Table 1 provides an outline of study data to be collected at each visit.

Additional visits that occur for adverse event assessment or adverse event follow-up following the index procedure will be recorded on an Unscheduled Visit and Adverse Event eCRF.

Table 1 Data Collection Schedule

Data Collection	Baseline	Procedure	6 Month	12 Month	18 Month	24 Month	36 Month	Un-scheduled ⁴
Informed Consent Obtained	X							
Inclusion/Exclusion Criteria Verified	X							
Pregnancy Test	X ¹							
Urinalysis	X ²							
Medical History	X							
Procedural Data		X						
Cystoscopy		X						
Post Void Residual Test	X ³		X	X	X	X	X	
Cough Stress Test	X ³		X	X	X	X	X	
24-Hour Pad Weight Test	X ³		X ⁵					
Medication Documentation	X	X	X	X	X	X	X	

Data Collection	Baseline	Procedure	6 Month	12 Month	18 Month	24 Month	36 Month	Un-scheduled ⁴
Patient Global Impression of Improvement (PGI-I)			X	X	X	X	X	
Surgical Satisfaction Questionnaire (SSQ-8)			X					
Visual Analog Scale for Pain (VAS Pain)	X	X ⁶	X					
Urinary Distress Index (UDI-6)	X		X	X	X	X	X	
Incontinence Impact Questionnaire (IIQ-7)	X		X	X	X	X	X	
Assessment of Adverse Events		X	X	X	X	X	X	X

¹To be performed within 30 days prior to the index procedure for women of childbearing potential

² To be performed within 30 days prior to the index procedure

³ To be performed within 6 weeks prior to index procedure

⁴ Any procedures performed relevant to the continence state of the subject should be documented on the follow-up form (e.g. PVR, urinalysis, or CST testing).

⁵ It is recommended that subjects complete pad weight testing within \pm 1 month of the scheduled visit.

⁶ The VAS Pain questionnaire will be completed by subjects at baseline, each day for the first 3 days following their index procedure, and at their 6 month follow-up visit.

5.1 Baseline Visit

The following study procedures will be performed at or prior to (as described in Table 1) the baseline visit.

- Informed Consent
- Pregnancy Test
- Urinalysis
- Medical History
- Post Void Residual Test
- Cough Stress Test
- 24-hour Pad Weight Test
- Medication Documentation
- Urinary Distress Index (UDI-6)
- Incontinence Impact Questionnaire (IIQ-7)
- Visual Analog Scale for Pain (VAS Pain)

5.2 Procedure Visit

The first surgical implant procedure after the subject is enrolled in the study is considered the index procedure. For newly implanted subjects a standard implant procedure is to be used as detailed in the Instructions for Use for Altis SIS or control product, as applicable. Implant procedure information will be collected as well as medication use during and after the procedure. Any deviation from the procedure should be identified on the appropriate procedure form and detailed on a study deviation form.

The subject will complete a VAS Pain questionnaire each day for the 3 days following their index procedure. The subject will be supplied with a postage paid return envelope to send the questionnaires back to the study site upon completion.

5.3 Follow-Up Visit Schedule

Data will be collected following the index procedure at 6 months, 12 months, 18 months, 24 months, and 36 months following the index procedure. Every attempt should be made to complete follow-up visits, however, if the subject cannot be seen in person, required questionnaires and pad weight testing kits should be mailed to the participant with a postage paid return envelope. If the follow-up visit cannot be completed within the visit window, the visit should still be completed as soon as possible and a study deviation form completed. All adverse events that are identified at any follow-up visit will be recorded on the appropriate adverse event form.

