5.3.1 Follow-up Visits: 6, 12, 18, 24, and 36 Month

Subjects are required to return to the office for required follow-up visits. The following procedures will be performed at each follow-up visit:

- Post Void Residual Test
- Cough Stress Test
- 24-hour Pad Weight Test
- Medication Documentation
- Patient Global Impression of Improvement (PGI-I)
- Urinary Distress Index (UDI-6)
- Incontinence Impact Questionnaire-Short Form (IIQ-7)
- Surgical Satisfaction Questionnaire (SSQ-8) – 6 months only
- Visual Analog Scale for Pain (VAS Pain) – 6 months only
- Assessment of Adverse Events

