7.5 Analysis of Primary Safety Endpoint

The number and proportion of subjects experiencing device- and/or procedure-related serious adverse events will be tabulated for each study group. Non-inferiority at 36 months will be calculated using a normal approximation test (Z-test) for a difference in binomial proportion with the following null and alternative hypotheses:

$$H_0: \pi_c - \pi_T \leq -0.10$$

$$H_a: \pi_c - \pi_T > -0.10$$

where π_c is the proportion of patients who have the primary safety endpoint during follow-up in the control group and π_T is the proportion of patients who have the primary safety endpoint during follow-up in the treatment group.

Handling of Missing Data

The primary analysis of this endpoint will include all available data from the ITT analysis population. Subjects that have not experienced a device- and/or procedure-related serious adverse event and who have missing data at 36 months will be assumed to be free of such an adverse event. However, the potential impact on the endpoint inference of all such subjects will be assessed via various sensitivity analyses that include best case, worst case and tipping point

analysis. In addition, a Kaplan-Meier product limit analysis that right censors subjects lost to follow-up will be conducted to further understand the potential impact of subject loss.

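### The mailed substitute for a missed visit names no adverse-event enquiry, and the Kaplan-Meier safety analyses as worded would not censor a woman followed that way

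*Protocol*

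**What the plan says.** **Visit content.** Protocol 5.3.1 states "Subjects are required to return to the office for required follow-up visits" and lists adverse-event assessment among the procedures at 6, 12, 18, 24 and 36 months. Table 1 agrees.

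**Fallback.** Protocol 5.3 provides that "if the subject cannot be seen in person, required questionnaires and pad weight testing kits should be mailed to the participant". The same section adds "All adverse events that are identified at any follow-up visit will be recorded on the appropriate adverse event form", and asks that an out-of-window visit still be completed as soon as possible. It does not mention a telephone enquiry, a mailed adverse-event form or a question about re-operation.

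**Lost to follow-up.** Protocol 3.7 applies this status to a woman who cannot be reached after at least three contact attempts: "To be considered lost to follow-up, all attempts to contact the subject must be documented and a registered letter must be sent".

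**Main safety analysis.** Under Protocol 7.5, women with no recorded event "who have missing data at 36 months will be assumed to be free of such an adverse event". Protocol 7.6.1 and 7.6.2 and SAP 12.6.2, 12.7.1 and 12.7.2 use the same rule, so it governs related serious events, related adverse events and revision/resurgery.

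**Sensitivity analyses.** SAP 12.6.2 says "a Kaplan-Meier product limit analysis that right censors subjects lost to follow-up will be conducted". It also says that the potential impact of "all subjects with missing primary safety endpoint data will be assessed via various sensitivity analyses", namely best case, worst case and tipping point. SAP 12.7.1 and 12.7.2 repeat both. Neither document says whether a mailed visit without an adverse-event assessment counts as missing.

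**The concern.** A site can follow Protocol 5.3 to the letter, receive a woman's 36-month questionnaires and pad test, and never have asked her about complications, hospital care or further surgery. The obvious example is a woman re-operated on at another hospital. SAP 13.1 to 13.5 describe the questionnaires as covering urinary condition, distress, impact, satisfaction and pain. None is described as eliciting adverse events or re-operations, and the satisfaction and pain instruments are not used after 6 months.

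Such a woman differs from a drop-out. A drop-out is censored in the Kaplan-Meier analysis. A woman who answers by mail is still in follow-up, so the censoring rule as worded passes her by.

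All three powered safety tests run to 36 months against fixed absolute margins. Unrecorded events in both arms lower both rates in proportion and so shrink the difference between them. If more events are missed in the Altis arm, the difference shrinks further. In an open-label, non-randomised cohort the arms may differ in how often women are followed remotely.

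**Working it through.** **1. The plan's own figure.** Inputs (Protocol 7.9.3, 7.9.5): 10% related serious-event rate in each group, margin 0.10, one-sided 0.025, 80% power, 20% attrition.

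n = (1.960 + 0.842)² × 2 × 0.10 × 0.90 / 0.10² = 7.849 × 0.18 / 0.01 = 141.3, so 142 per group. This matches SAP 10.2.

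142 / 0.80 = 177.5, so 178 per group. This matches Protocol 7.9.3.

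**2. How a woman followed by mail at 36 months is handled, if the site has learned of no event**

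| Analysis | Rule as written | Her status |
|---|---|---|
| Three main tests | No recorded event counts as event-free, including when 36-month data are missing | Event-free, whether or not she is classed as missing |
| Kaplan-Meier | Censors those lost to follow-up | Not censored |
| Best case, worst case, tipping point | Covers missing endpoint data | Not stated; can be read to include her |

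**3. Effect on the primary safety test.** Let f be the share of women followed only by mail and s the share of their events never recorded. Neither is in the documents; both are assumptions.

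Recorded rate = true rate × (1 − f × s).

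Put the truth at the margin: 10% control, 20% Altis, 178 per arm. Non-inferiority is declared if the lower 95% Wald limit for control minus Altis exceeds −0.10. The probability of declaring it is obtained by summing over all binomial outcomes.

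Worked case, f = 0.20 and s = 1/2 in both arms:
- Recorded rates are 0.10 × 0.90 = 0.09 and 0.20 × 0.90 = 0.18, a difference of 0.09.
- SE = √(0.09 × 0.91/178 + 0.18 × 0.82/178) = 0.0359.
- The normal approximation gives Φ(0.01/0.0359 − 1.96) = 4.6%. Exact enumeration gives 5.0%.

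With full ascertainment the exact figure is 2.7% (2.5% by the normal approximation). Exact results for f = 10% / 20%:

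| Share of their events unrecorded (s) | Both arms | Altis only | Control only |
|---|---|---|---|
| 1/6 | 3.0% / 3.3% | 3.3% / 4.0% | 2.5% / 2.2% |
| 1/3 | 3.3% / 4.1% | 4.0% / 5.9% | 2.2% / 1.8% |
| 1/2 | 3.7% / 5.0% | 4.9% / 8.4% | 2.0% / 1.4% |

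Here s = 1/3 corresponds to only months 24 to 36 being unseen under a constant hazard (12/36), and s = 1/6 to half of those events reaching the site another way.

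**4. Secondary related-event test.** With true rates of 20% and 35%, margin 0.15, f = 20% and s = 1/2 in both arms, false non-inferiority is 5.2% against 2.5% with full ascertainment.

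**5. In counts.** Suppose 18/178 serious events are recorded in each arm. Six further Altis events (24/178) give a difference of −0.0337 with SE 0.0341, so the lower limit is −0.0337 − 1.96 × 0.0341 = −0.1006, and non-inferiority fails. At 10% mail-only, about 18 Altis women are involved, and six unrecorded events would mean a third of them. That is more than the assumed rates would produce: even at a true rate of 20%, 18 women have 3.6 events expected in total.

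**The case against.** **Protocol 5.3 does not waive the assessment.** It says what to mail. It does not forbid a call, and Table 1 still lists adverse-event assessment at each visit. Other routes exist. Protocol 14.1 says "Collection of Adverse Events will begin at the time the first incision is made for the index surgical procedure and will continue" until participation ends; 5.4 has all revisions and explants recorded; 5.3.2 captures events at unscheduled visits; and Table 3 sets prompt reporting of serious events. The mailed pad test also bears on recurrent incontinence, one of the listed events. This stands in part: it rules out saying that such a woman certainly has no ascertainment. But these routes work only if the site learns of the event, and none requires it to ask a woman followed by mail.

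**The sensitivity analyses may already reach her.** A reader might infer that returned forms make her an observed case and put her outside every planned sensitivity analysis. The documents do not support that. The best-case, worst-case and tipping-point analyses are tied to missing safety endpoint data, and a returned questionnaire or pad test is not a safety assessment. On a natural reading she is included. No text says that a returned form makes her observed, and the main result is the same under either classification. What is left is the Kaplan-Meier wording and the undefined meaning of missing.

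**The size rests on assumptions, and the bias need not favour Altis.** Both are correct. Mail follow-up confined to the control arm makes the test conservative, and nothing in the documents suggests that remote follow-up would be commoner with Altis.

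**Conclusion.** The gap is real but limited. As written, the remote-visit procedure names no adverse-event or re-operation enquiry, the main tests score a woman with no recorded event as event-free, and the Kaplan-Meier rule does not censor her if she returns her forms. Her place in the other sensitivity analyses is unstated.

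The likely effect is under-ascertainment that favours non-inferiority when it occurs in both arms or mainly in the Altis arm. With true serious-event rates of 10% and 20%, 178 per arm, 10–20% mail-only and one sixth to one half of their events unrecorded, false non-inferiority goes from 2.7% to 3.0–5.0% (both arms), 3.3–8.4% (Altis only) or 1.4–2.5% (control only). These figures show how the error would respond. They are not estimates for this study, and the true effect could be negligible if few visits were done by mail. This is a cheap improvement to the plan, not a fault that invalidates the safety comparison.

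**What to change.** **Protocol 5.3.** Require an adverse-event and re-operation enquiry, by telephone or mailed form, at any visit not done in person. Record on the eCRF whether it was completed, its date and its mode.

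**SAP 12.6.2, 12.7.1 and 12.7.2.** Define missing 36-month safety data by the last completed adverse-event assessment, not by the return of any form. Censor women without an event at that date in the Kaplan-Meier analyses. If data collection has ended, this part can still be applied wherever assessment dates can be recovered.

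**Cost.** One protocol sentence, one eCRF item and one SAP definition. Sites make a short extra contact with women to whom they are already mailing materials. A few more women will count as missing or censored in the sensitivity analyses. The sample size of 178 per group does not change.
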